4.0 Terms and Abbreviations

Abbreviation	Term
AE	Adverse Event
CBC	Complete Blood Count
CLIA	Clinical Laboratory Improvement Amendments
DICOM	Digital Imaging and Communications in Medicine
FIS	Fisetin
MRI	Magnetic Resonance Imaging
OA	Osteoarthritis
PRO	Patient Reported Outcome
PHI	Protected Health Information
PTOA	Post-traumatic Osteoarthritis
ROM	Range of Motion
SASP	Senescence Associated Secretory Phenotype
SCAPs	Senescent-Cell Anti-Apoptotic Pathways
SOC	Standard of Care
SPRI	Steadman Philippon Research Institute
TSC	The Steadman Clinic

5.0 Introduction

5.1 Background and Significance

The Steadman Clinic (TSC) and the Steadman Philippon Research Institute (SPRI) are proposing a Phase 1-2 prospective clinical study to collect safety and efficacy data on the use of Fisetin (FIS), which is a nutritional supplement and senolytic agent, in treating patients with Osteoarthritis (OA) of the knee. This study is entitled: *Senolytic Drugs Attenuate Osteoarthritis-Related Articular Cartilage Degeneration: A Clinical Trial*.

Recently, several senolytic compounds that selectively kill senescent cells in vitro and in vivo without affecting quiescent or proliferating cells were identified¹. These senolytic drugs target and inhibit anti-apoptotic pathways that are upregulated in senescent cells, thereby inducing apoptotic cell death and abrogating systemic Senescence-Associated Secretory Phenotype (SASP) factors.

As further discussed in 5.3 of this protocol, we have demonstrated in pre-clinical studies that treatment with senolytic drugs including (FIS, Dasatinib (D), Quercetin (Q) and Alvespimycin) can reduce the incidence/severity of many age-related disorders, including OA in naturally aged and progeroid mice (accelerated aging). These studies have shown that senolytic treatment (D/Q and FIS) can delay articular cartilage degeneration in a murine model of natural and accelerated (progeria) aging.

Based on this promising pre-clinical data, we believe it may be possible to delay or even reverse joint degeneration, damage to ligaments, menisci, cartilage, thereby resulting in the extension of high-level function and preservation of quality of life.

In this randomized, double-blind, placebo-controlled clinical trial, we intend to measure and compare safety via the gathering of all adverse events and preliminary evidence of efficacy through recording of SASP, inflammatory biomarkers and senescent cells. In addition, magnetic resonance imaging (MRI) exams, self-reported outcomes, functional performance and other relevant clinical data will be gathered. Possible correlation among outcomes, both structural and non-structural, will be described.

Each subject is to be followed for 18 months.

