
Endpoints:
	
Primary Endpoint:
 
Occurrence of adverse events.
 
Secondary Endpoints
 
Statistically significant as compared to placebo:
 
 1. Improvement in serum measures of inflammation and cartilage degenerating senescence associated secretory phenotype (SASP) markers; 2. Improvement in lower-extremity kinematic testing with video-motion analysis; isokinetic dynamometry testing, functional performance testing, range of motion (ROM);

	
 3. Improvement in patient reported outcomes (PROs), including: IKDC, Lysholm, TEGNER, WOMAC and SF-12 surveys; 4. Improvement in the quality of articular cartilage in the knee joint as measured by T2 and T1rho relaxometry; 5. Days from day one of Study Medication intake to conversion to alternative therapy. 
Additionally, we will review and discuss any possible correlation among secondary endpoint results.

Inclusion Criteria	
Subjects will be included if all the following criteria are met:
 
 1. Are male or female, ages 40-80; 2. Are willing to comply with all study related procedures and assessments; 3. Are ambulatory as defined by ability to complete functional performance testing; 4. Radiographic evidence of Kellgren-Lawrence grade II-IV osteoarthritis in one or both knees; 5. Scores 4-10 on the Numerical Rating Scale (NRS) for pain; 6. Stable dose of screening/baseline medications for at least 2 months prior to the anticipated date of study drug dosing.
Exclusion Criteria:	
Subjects will be excluded if any of the following criteria are met:
 
 1. Females who are nursing, pregnant or planning to become pregnant during the duration of study drug dosing; 2. Males who do not wish to abstain from sex or use contraceptive protection during study drug dosing and for 2 weeks after the last dose; 3. Subjects who do not have the capacity to consent themselves; 4. Subjects who are unable to tolerate oral medication; 5. Subjects having previously undergone any of the following treatments in the stated time window: 
 -Surgery on the Study Knee in the past 6 months;

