8.2 Study Endpoints

8.2.1 Primary Endpoint:

1. Occurrence of adverse events.

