12.0 Study Management of Adverse Events

12.1 Definition

An adverse event (AE) is any untoward medical occurrence in a subject administered a Study Medication and which does not necessarily have a causal relationship with this treatment. An AE can therefore be any unfavorable and unintended sign (including an abnormal laboratory finding), symptom, or disease temporally associated with the use of whether or not related to the Study Medication (ICH E2A II/A/1, 21 CFR 312.32).

All pre-existing medical conditions will be recorded on the medical history study document. Starting with the administration of the Study Medication any new experience that was not present at baseline or worsening of an event present at baseline in intensity or frequency, is considered an adverse event.

Note: Unchanged, chronic conditions are NOT adverse events and should not be recorded.

It is recognized that subjects will exhibit (throughout follow-up) symptoms of the underlying disease process of that fluctuates in severity and duration.

Adverse events will include those occurrences, which when compared to before treatment meets any of the following criteria:

- Represent a new event or escalation of an event;
- Require a new escalation in treatment;
- Lasts longer;
- Experienced more frequently;
- More intense;
- Different in character (e.g. stabbing vs. ache);
- Experienced in a different part of the body; and/or
- Brought on by activity that previously did not cause the symptom.

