15.5 Endpoints

15.5.1 Primary Endpoint

The safety of FIS administration is the primary endpoint of this study. All adverse events will be compared by category of description incidence, relatedness to treatment, severity, duration and expectedness. The occurrence of non-serious and serious and unexpected adverse events will be compared between treatment groups. Bivariate analysis will be performed between group and each safety variable of interest independently. When comparing the two treatment groups, dichotomous (yes/no) endpoints will be assessed for association using Fisher's exact test. Adverse events and symptoms that may occur multiple times in a single subject will be analyzed as count variables, and group differences will be assessed using simple Poisson regression or simple negative binomial regression.

This is a small Phase I/II trial in which to assess safety, thus we will report all safety data thoroughly and aim to liberally identify potential side-effects and risks that may warrant close study in future, larger trials. No adjustments will be made for multiple comparisons in this set of safety endpoints.

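### The all-AE comparison behind the safety hypothesis includes worsening knee OA symptoms that fisetin is expected to reduce, so knee benefit or OA background can dilute a drug-specific excess

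*Combined protocol and SAP*

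**What the plan says.** Section 5.1 gives the general intention: "we intend to measure and compare safety via the gathering of all adverse events". The primary endpoint in section 8.2.1 is "Occurrence of adverse events", without restriction by cause. Section 15.1 states the matching hypothesis: the AE rate on fisetin will not exceed that on placebo. No margin is given.

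Section 12.1 sets what counts. Its general rule is that "worsening of an event present at baseline in intensity or frequency, is considered an adverse event". It then acknowledges that symptoms of the underlying disease fluctuate during follow-up, and continues: "Adverse events will include those occurrences, which when compared to before treatment meets any of the following criteria". The list covers greater intensity, greater frequency, longer duration and "Require a new escalation in treatment". Any one criterion is enough. The only exclusion is that "Unchanged, chronic conditions are NOT adverse events and should not be recorded". Study-knee OA is not exempted.

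The same symptoms are efficacy outcomes. Section 15.5.2.3 tests whether treatment group predicts pain reduction and analyses the knee questionnaires. Secondary endpoint 5 is "Days from day one of Study Medication intake to conversion to alternative therapy".

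Section 15.5.1 plans comparisons of AEs by category, relatedness, severity, duration and expectedness, and adds that "The occurrence of non-serious and serious and unexpected adverse events will be compared between treatment groups". Yes/no endpoints use Fisher's exact test; repeated events use Poisson or negative binomial regression. No analysis separates study-knee OA events from the rest.

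**The concern.** A knee-pain flare on placebo adds to the AE count, and a flare prevented by fisetin removes one. Nausea or diarrhea caused by fisetin adds one. In the overall rate these offset each other. If fisetin helps the knee and also has side effects, the overall ratio moves towards 1. If it does not help the knee, OA events still add background to both arms and make a drug-specific excess harder to see.

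Safety is the primary purpose of the trial, and section 15.5.1 sets out to identify possible side effects liberally. The summary that answers the hypothesis in 15.1 is the one least able to do so.

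**Working it through.** **The plan's own figure.** Section 15.6 sizes the trial on T1rho with a standardized difference of 0.73, two-sided alpha 0.05 and 80% power: n = 2(1.960 + 0.842)²/0.73² = 2 × 7.85/0.533 = 29.5, so 30 per group. This reproduces. Adding 6 per group gives 36, as in section 6.0; the cap of 100 would allow 50 per arm. The documents give no AE rate, margin or power for the primary safety endpoint, so every event rate below is an assumption.

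**Do the planned breakdowns separate the two kinds of event?**
- Expectedness: no. Section 12.2.5 places disease-process events and the section 13.0 risks, which include nausea, diarrhea, vomiting and fatigue, in the same expected class.
- Relatedness: partly. Section 12.2.3 asks the Principal Investigator to weigh association with the underlying disease. That is a causal judgement about each event.
- Category: possibly, but 15.5.1 defines no categories.
- Procedures: section 12.2 says that the AE term is the reason for a procedure, not the procedure. An injection or operation therefore enters only through the symptom that prompted it.

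**Event counts, 36 per arm, one year.** Let A be OA events and B other events per subject-year on placebo, and c the proportion by which fisetin cuts OA events. Fisetin adds 0.5 side-effect events per subject.
- Pooled means: m0 = A + B on placebo; m1 = A(1 − c) + B + 0.5 on fisetin.
- Excluding OA: B against B + 0.5.
- Between-subject variation: gamma frailty with variance 0.5, separately for OA and other events. A component with mean m then has variance m + 0.5m²; the added side effects have variance 0.5.
- SE of the log ratio = √[(V0/m0² + V1/m1²)/36]; z = ln(m1/m0)/SE; two-sided test at 0.05.

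Excluding OA, B = 0.5: V0 = 0.5 + 0.5 × 0.25 = 0.625 and V1 = 1.125. SE = √[(2.5 + 1.125)/36] = 0.317, z = 0.693/0.317 = 2.18, power about 59%. Simulation gives 61%.

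Pooled, A = 1.5, c = 0: V0 = 2.625 + 0.625 = 3.25 and V1 = 3.75. SE = √[(3.25/4 + 3.75/6.25)/36] = 0.198, z = 0.223/0.198 = 1.13, power about 20%. Simulation gives 21%.

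Powers below are from simulation; repeat runs differ by about a percentage point.

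| A | B | OA cut | Pooled means | Pooled ratio | Pooled power | Ratio and power excluding OA |
|---|---|---|---|---|---|---|
| 1.5 | 0.5 | 33% | 2.0 v 2.0 | 1.00 | 6% | 2.00, 61% |
| 1.5 | 0.5 | 20% | 2.0 v 2.2 | 1.10 | 8% | 2.00, 61% |
| 1.5 | 0.5 | 0% | 2.0 v 2.5 | 1.25 | 21% | 2.00, 61% |
| 0.25 | 0.5 | 20% | 0.75 v 1.20 | 1.60 | 43–44% | 2.00, 61% |
| 0.5 | 1.5 | 20% | 2.0 v 2.4 | 1.20 | 15–16% | 1.33, 25% |

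The 6% in the first row is essentially the error rate of the test. Exact cancellation needs A × c = 0.5: a one-third cut when A = 1.5, a complete cut when A = 0.5, and it is impossible when A = 0.25. At 50 per arm the second row becomes about 9% against 75%.

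**Any AE, Fisher's exact test, 36 per arm, significant in the direction of harm.** With independent event types, P(any AE) = 1 − (1 − p_OA)(1 − p_other). Take p_other as 10% on placebo and 40% on fisetin; alone, this has 80% power.
- OA 30% in both arms: 37% v 58%, power 32%.
- OA 50% in both arms: 55% v 70%, power 18%.
- OA 50% v 37.5%: 55% v 62.5%, power 5.5%.
- OA 50% v 25%: 55% v 55%, power about 1%.

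**The case against.** The best defence is that 15.5.1 is a set of tables, not one pooled test. It compares relatedness, severity and each safety variable on its own. An excess of vomiting would show in its own comparison, where knee benefit cannot cancel it. A blinded investigator would probably call most OA flares unrelated. No rule lets a pooled ratio near 1 override those tables. This stands, and it limits the point to the overall rate and the hypothesis in 15.1. A reader might infer that a harmful drug would be declared safe; the plan contains no such decision rule.

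A reader might also infer that steroid injections, regenerative treatments or surgery are themselves counted as AEs, so that endpoint 5 and the safety endpoint are the same events. Section 12.2 does not support that. The overlap is in symptom worsening, including worsening that calls for new treatment.

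The assumed rates matter too. Unchanged chronic conditions are excluded, and entry requires baseline pain of 4 to 10, so frequent OA AEs are not a given. When OA events are the minority, much of the low power comes from the small sample, as the last table row shows. One sentence in 12.2 ties recording to the medication period, while the rest of that section and the visit lists call for AE assessment at follow-up visits. These need reconciling. On the narrow reading, 1.5 OA events per year over 32 days is only 1.5 × 32/365 = 0.13 per subject, and little dilution would remain.

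Finally, comparing all AEs is a legitimate default, and knee worsening could itself be drug harm. That argues against replacing the all-AE comparison, not against adding to it.

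**Conclusion.** The point holds for the overall AE-rate comparison. Sections 12.1, 15.1 and 15.5.1 together put hypothesised benefit and possible harm into one count, and expectedness cannot separate them. Relatedness and the individual comparisons may still reveal a drug-specific excess, so not every safety table is affected.

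The usual consequence is dilution; full cancellation is the extreme case and needs both frequent OA events and a sizeable knee benefit. Under the assumed rates, the loss of power runs from modest (25% to about 15%, or 61% to about 44%) to large (61% to between 6% and 21%). These figures rest on assumed event rates, one year of AE recording, 36 subjects per arm and independence between OA and other events. They show a range and do not predict what this trial will see. The change is worth making because it uses data already collected and serves the stated aim of 15.5.1.

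**What to change.** In section 15.5.1:
- Classify each AE as study-knee OA symptom worsening or other. Do this blinded, and before the Group A and Group B codes in 15.8 are added.
- Prespecify the between-group occurrence and count comparisons of AEs excluding study-knee OA events. Report them beside the all-AE comparison and a table of study-knee events.
- State that the hypothesis in 15.1 is read from both comparisons.

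Keep recording every event, and keep the all-AE comparison. Drug-caused knee worsening then stays visible in the total and in the study-knee table. The recording-period wording in 12.2 should be reconciled at the same time.

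The cost is one classification field on the AE form, a few lines of text and one further comparison without multiplicity adjustment, which matches how 15.5.1 already treats safety. It should be settled before group codes are attached, because a split made later would look driven by the data.

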5.2 Rationale

Aging is associated with the accumulation of senescent cells, which have lost their ability to proliferate and resist apoptosis. Aging cells produce a SASP consisting of potent pro-inflammatory and stress inducing factors²⁻⁵. OA, along with a litany of other age-related pathologies, is associated with cellular senescence, which is thought to promote aging via the chronic induction of inflammation²⁻⁶.

OA is a debilitating and costly joint disease that affects millions of individuals each year for which there are no available disease modifying therapies^{7,8}. Several studies have shown that spontaneous age-associated and post-traumatic OA (PTOA) is characterized by an increase in senescent chondrocytes within the joint capsule⁹⁻¹³ that is thought to promote early inflammation and OA pathogenesis. Importantly, it was found that injection of senescent cells into the joint capsule of healthy mice could alone induce OA-like conditions in mice including severe cartilage degeneration, erosion of femoral condyles, subchondral bone structure alteration, osteophyte formation, and meniscal damage¹⁴. Inversely, other groups have shown that local clearance of senescent cells genetically within the intra-articular space significantly reduces development of injury-induced OA and promotes a pro-regenerative environment¹⁵. Thus, the link between cellular senescence and OA pathogenesis is strong, highlighting senolytic drugs as a very appealing and innovative approach to prevent or treat OA.

There are currently three Phase II clinical trials designed to investigate FIS in senescence associated diseases, including frailty, inflammation, diabetic and chronic kidney disease NCT03430037, NCT03675724, NCT03325322. To date there have been no human studies that have evaluated senolytic drugs for the treatment of knee OA.

5.3 Pre-Clinical Data

The following pre-clinical studies present an animal model for the study of OA, a proof of concept connection between cell senescence and loss of chondrogenic capacity, proteoglycan content, which may lead to OA, as well as the potential protective effect of senolytic agents.

5.3.1 Progeroid Musculoskeletal Symptoms in Z24^{-/-} Mice Are Associated with Increased Senescent Cell Burden

Muscle derived stem/progenitor cells (MDSPCs) are a population of adult muscle progenitors that the SPRI laboratory uses for various regenerative medicine applications. MDSPCs isolated from skeletal muscle of 2 months old Z24^{-/-} Mice with progeroid symptoms were found to have significantly elevated β -galactosidase (β -gal⁺) cells when compared to Wild-Type (WT) healthy control cells. β -gal is a

hydrolytic enzyme whose activity is upregulated during aging and an established marker for cellular senescence¹⁶. Further, β -gal expression is associated with increased expression of other senescence associated cell cycle regulator transcription factors, including p16 and p21. These transcripts are elevated in senescent cells and keep them in a non-proliferative state, a hallmark of senescence. Senescent cells were also detected in gastrocnemius muscle from progeroid Z24^{-/-} mice.

It has been reported that skeletal muscle histopathology are seen with a dysfunction of MDSCs in Z24^{-/-} mice¹⁷. Therefore, we believe these musculoskeletal pathologies observed in **Z24^{-/-} mice** are associated with increased senescent cell burden.

5.3.2 Primary Chondrocytes from Progeroid Z24^{-/-} Mice Exhibit Reduced Chondrogenic Capacity *in vitro* and Spontaneous Loss of Articular Cartilage Proteoglycan Content *in vivo*.

Z24^{-/-} mice are deficient in the metalloprotease Zmpste24, which results in the accumulation of unprocessed Lamin A, very similar to progerin in patients with Hutchinson-Gilford progeria syndrome (HGPS). This causes blebbing of the nuclear membrane¹⁸. Disruption of the nuclear envelope due to Lamin A accumulation leads to destabilization of heterochromatin, DNA damage, and eventual cell cycle arrest and senescence¹⁹. Chondrocytes are the sole cell type in articular cartilage and are responsible for maintaining the specialized extracellular matrix proteoglycan content on joint surfaces¹⁹. To gauge the effects of Zmpste24 loss specifically in chondrocytes, primary costal chondrocytes from 2-month-old Z24^{-/-} mice were isolated as previously described²⁰. As expected, chondrocytes from Z24^{-/-} mice lacked Zmpste24 expression, exhibited nuclear blebbing and were found to have reduced expression of type II collagen (Col2).

Accordingly, pellet culture of isolated chondrocytes were significantly smaller with decreased Col2 signal and toluidine blue stain intensity indicating decreased chondrogenic capacity. These data suggest that progeroid Z24^{-/-} chondrocytes are sensitive to senescence and dysfunction which may initiate or potentiate OA. Indeed, safranin O staining of Z24^{-/-} articular cartilage revealed obvious loss of proteoglycan content versus WT at only 5 months of age.

5.3.3 Z24^{-/-} Mice Are More Sensitive to Injury-Induced OA Versus Age-Matched WT Animals.

PTOA accounts for roughly 12% of OA cases. Although associated with acute initiation, PTOA is characterized by similar cellular phenotypes to age-associated OA^{21,22}. Surgical destabilization of the medial meniscus (DMM) is an established method to model post-traumatic OA that allows for the immediate initiation of OA with more severe phenotypes including overt inflammation, cartilage

degeneration, and osteophyte formation. These effects can be detected histologically and radiologically²³. Given that Z24^{-/-} animals showed diminished proteoglycan content, an early sign of OA, we hypothesized that they might be more sensitive to injury- induced OA.

With this in mind, a small cohort of Z24^{-/-} and WT mice received DMM as described²³, then were sacrificed at 12 weeks. Changes in their articular cartilage was examined histologically.

As expected, DMM in WT mice resulted in decreased proteoglycan content within the articular cartilage as well as elevated MMP-13 and ADMTS-5 expression (ECM degrading enzymes up-regulated during OA). However, cartilage degeneration was significantly worse in Z24^{-/-} mice, when compared to normal mice, demonstrating their sensitivity to injury-induced OA.

These data highlight the utility of the Z24^{-/-} model to evaluate senolytic therapies in moderate progressive symptomatic OA as well as severe more aggressive injury-induced OA.

5.3.4 D/Q Protects from Spontaneous Proteoglycan Loss and OA-Associated ADMTS4 Expression in Articular Cartilage Of Z24^{-/-} Mice.

As a proof of concept, a pilot study was conducted with Dasatinib + Quercetin (D/Q) (5 mg/kg; 50 mg/kg) using Z24^{-/-} mice. Mice were administered D/Q via oral gavage as a single dose (D/Q_{sin}) at 4 months of age, or monthly dose starting at 2 months of age (D/Q_{mul}) prior to sacrifice at 5 months old.

Quite surprisingly, a single dose of D/Q alone was enough to mitigate proteoglycan loss in articular cartilage of Z24^{-/-} mice. These effects were even more dramatic in mice treated with multiple doses of D/Q demonstrating a dose response to D/Q treatment throughout the short 3 months treatment window. In addition, Z24^{-/-} mice in the D/Q_{mul} group were found to have decreased ADMTS-4 positive cells indicative of less ECM degradation.

While only preliminary, and from a single time point (5 months), these data strongly suggest that senolytic drug treatment may facilitate the retention of articular cartilage proteoglycan content and possibly mitigate age-related OA pathogenesis.

